#### **4.9.4 Safety Analysis**

Information on the timing, severity, relationship to premedication, relationship to OCR therapy, effect on therapy, and degree of seriousness of adverse events will be collected from and summarized for all patients.

#### **4.9.5 Missing Data**

Baseline characteristics and outcomes for patients who followed protocol and completed the study, violated protocol, and discontinued the study will be reported separately. The reasons for discontinuing or violating protocol will be reported and any influence on the trial results will be discussed. Any other irregularities that result in missing data will be fully identified and discussed.

For the primary endpoint using the intention-to-treat population, the missing data mechanism will be examined and multiple imputation or best/worst imputation will be used, assuming missing at random. For the primary endpoint, assessed at day 0, we expect missing data will be limited.

#### **4.9.6 Determination of Sample Size**

Based on the results of the OPERA I and II trials, we assume that 25% of patients in the diphenhydramine arm and 25% of patients in the cetirizine arm will experience mild to severe IRRs during or after receiving the first infusion on day 0. Assuming that a 30% absolute difference (i.e. margin = - 0.30) in the proportion of patients with IRRs between premedication groups is the maximum relevant difference when holding that cetirizine is not inferior to diphenhydramine, 26 patients per arm are needed to achieve 80% power with a one-sided significance level of 0.05. As this is a pilot study, we allow a large margin to establish some evidence of non-inferiority. The two-sample proportion test for non-inferiority in the R package Trial Size was used for the calculation.

### **4.10 DATA QUALITY ASSURANCE**

Accurate, consistent, and reliable data will be ensured through the use of standard practices and procedures.

## **5. REPORTING OF ADVERSE EVENTS**

At the time of consenting, each patient will be given the names and telephone numbers of the study personnel for reporting AE's. The investigator must conduct thorough

assessment to determine the severity of the AE and the relationship to the premedication and OCR. The investigator must review the laboratory findings for significance (all out of range values must be assessed as clinically significant or not clinically significant) and sign and date the laboratory report. All clinically significant laboratory findings must be reported as adverse events. MS related symptoms are not to be reported as AEs unless, in the opinion of the investigator, the symptoms are unusually serious and relevant. Any AE of severity moderate or higher, requires follow up until resolution or stabilization by the treating investigator beyond the final study contact as part of standard care.

All AEs should be recorded in the patient's AE case report form regardless of severity or relationship to the premedication or OCR.

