### **3.2 RATIONALE FOR STUDY DESIGN**

Shortly after the approval of OCR, we followed the premedication protocol used in OPERA I and II which included 100mg of methylprednisolone, 1 gram of acetaminophen, and 50mg of IV diphenhydramine. However, many patients experienced extreme sedation which caused severe drowsiness and impaired their ability to function, drive, or work during and after the infusion, and even the following day. As a result, we have decreased the dose of diphenhydramine to 25mg administered either IV or orally which has resulted in less, but still marked, drowsiness. Newer antihistamines such as cetirizine may be better tolerated; however, there is no evidence that they will be as effective in minimizing infusion reactions.

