#### Suggested Management of IRRs

All CD20+ depleting agents administered via the intravenous route, including OCR, have been associated with acute IRRs. Symptoms of IRRs may occur during any ocrelizumab infusion, but have been more frequently reported during the first infusion. Physicians should alert patients that IRRs can occur within 24 hours of the infusion. These reactions may present as pruritus, rash, urticaria, erythema, throat irritation, oropharyngeal pain, dyspnea, pharyngeal or laryngeal edema, flushing, hypotension, pyrexia, fatigue, headache, dizziness, nausea, and tachycardia.

Patients should be observed for at least one hour after the completion of the infusion for any symptom of IRR. They will be informed about the possibility of delayed post-infusion symptoms and instructed to contact their study physician if they develop such symptoms.

Hypotension, as a symptom of IRR, may occur during ocrelizumab infusions. Therefore, withholding of antihypertensive treatments should be considered for 12 hours prior to and throughout each ocrelizumab infusion.

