### **Infusion-Related Reactions (IRRs)**

Adverse events that occur during or within 24 hours after OCR administration and are judged to be related to OCR infusion should be captured as a diagnosis (e.g., "infusion-related reaction" or "anaphylactic reaction") on the Adverse Event eCRF. If possible, avoid ambiguous terms such as "systemic reaction." Associated signs and symptoms should be recorded on the dedicated Infusion-Related Reaction eCRF. If a patient experiences both a local and systemic reaction to the same dose of OCR, each reaction should be recorded separately on the Adverse Event eCRF, with signs and symptoms also recorded separately on the dedicated Infusion-Related Reaction eCRF.

Investigators should consider a local IRR for any symptoms affecting the skin and localized to only one place. Any other IRR should be considered systemic.

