### Adverse Events

An AE is any unfavorable and unintended sign, symptom, or disease temporally associated with the use of the premedication, OCR, or other protocol-imposed intervention, whether or not there is a causal relationship with OCR or the premedication.

This includes the following:

- AEs not previously observed in the patient that emerge during the protocol-specified AE reporting period.
- Complications that occur as a result of protocol-mandated interventions (e.g., procedures such as OCR infusions).
- If applicable, AEs that occur after signing consent, prior to assignment of study treatment associated with medication washout, no treatment run-in, or other protocol-mandated intervention.
- Preexisting medical conditions (other than the condition being studied) judged by the investigator to have worsened in severity or frequency or changed in character during the protocol-specified AE reporting period.

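### The exemption of MS-related symptoms from AE reporting has no carve-out around infusions, so post-infusion fatigue, drowsiness or dizziness can drop out of the AE record and possibly out of the IRR count

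*Combined protocol and SAP*

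**What the plan says.** **The exemption.** Section 5 (Reporting of Adverse Events) says: "MS related symptoms are not to be reported as AEs unless, in the opinion of the investigator, the symptoms are unusually serious and relevant". Section 3.4 (Safety Plan) repeats it. Neither place gives a criterion for calling a symptom MS related or sets a time limit.

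**The general rule.** The same part of Section 5 adds: "All AEs should be recorded in the patient's AE case report form regardless of severity or relationship to the premedication or OCR". Section 5.1 defines an AE by its timing relative to the premedication, OCR or another protocol intervention, "whether or not there is a causal relationship with OCR or the premedication". Its item on worsening of existing disease leaves out MS: "Preexisting medical conditions (other than the condition being studied) judged by the investigator to have worsened in severity or frequency".

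**IRRs.** Section 3.4 (Suggested Management of IRRs) lists possible presentations, including "flushing, hypotension, pyrexia, fatigue, headache, dizziness, nausea, and tachycardia". Section 5 (Infusion-Related Reactions) treats an IRR as an adverse event during or within 24 hours after OCR that is judged related to it, and adds: "Associated signs and symptoms should be recorded on the dedicated Infusion-Related Reaction eCRF". The primary outcome (Section 3.3.1) is the proportion of patients with an IRR at the day 0 infusion, documented in the clinic and at the call on the next business day.

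**Tolerability.** Section 3.2 says that oral or IV diphenhydramine 25 mg has been used, "which has resulted in less, but still marked, drowsiness". TSQM, SSS and VAS-F are given once within 2 hours after each infusion (Sections 3.1 and 4.5.1) and compared between arms (Section 4.9.3). Section 4.9.4 promises a summary of "Information on the timing, severity, relationship to premedication, relationship to OCR therapy" and other AE attributes.

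**The concern.** The same symptom can fall under two rules. The protocol handles fatigue as part of MS, with MFIS and VAS-F at screening, and also names it as a possible IRR presentation. A patient with MS who is more tired or dizzy after an infusion may have an MS symptom, a premedication effect or an IRR. If the investigator chooses the first and the symptom is not unusually serious, no AE entry is made.

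Two things are at stake. The first is the descriptive AE record, the only place where a symptom is attributed separately to premedication and to OCR. The second is the IRR count behind the primary endpoint, because Section 5 derives IRRs from AEs and the planning rate in Section 4.9.6 includes mild ones. No masking is described in Sections 3.1, 4.2 or 4.3, so the judgement can be made knowing the arm, and an exempted symptom leaves no AE entry by which a difference in practice could be seen.

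**Working it through.** **1. Which data the exemption can reach**

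| Information | Where it is captured | Can the exemption remove it? |
|---|---|---|
| Sleepiness, fatigue and satisfaction within 2 hours of infusion | SSS, VAS-F, TSQM | No |
| Fatigue or drowsiness later that day or the next day | Next-business-day call, which seeks infusion reactions and other AEs and repeats no scale | Yes |
| Dizziness at any time | AE or IRR record only; no scale is planned | Yes |
| Relationship to premedication and to OCR | AE record only (Section 4.9.4) | Yes |
| IRR yes/no and severity | Infusion reaction assessment, call, AE and IRR forms | Possibly |

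The second row matters because Section 3.2 describes sedation lasting into the following day. It does so for the 50 mg IV dose, not the 25 mg oral dose used here.

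The last row says possibly for two reasons. Nothing instructs investigators to apply the exemption to IRRs. A patient is also lost from the count only if every reaction symptom is set aside, so someone with a rash as well as fatigue still counts.

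**2. The plan's own sample size**

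Inputs (Section 4.9.6): 25% in each arm, margin 0.30, one-sided 0.05, power 80%.

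n per arm = [2 × 0.25 × 0.75] × (1.645 + 0.842)² / 0.30² = 25.76, rounded up to 26. This reproduces the stated figure. At 26 per arm the normal-approximation power is 80.3%. The AE rule does not enter this calculation.

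**3. Direction of the effect if IRRs are under-recorded**

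Assumptions: true rates at the margin (25% diphenhydramine, 55% cetirizine), 26 per arm, the same share s of IRRs recorded in both arms, and a Wald 90% interval whose lower limit must exceed -0.30. The plan does not name the interval method, so Wald is also an assumption. The recorded difference is s × 30 points. The chance of declaring non-inferiority is summed exactly over all pairs of binomial counts.

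| Share recorded (assumed) | Recorded rates | Recorded difference | Chance of declaring non-inferiority |
|---|---|---|---|
| 100% | 25.0% vs 55.0% | 30.0 points | 4.9% |
| 90% | 22.5% vs 49.5% | 27.0 points | 8.3% |
| 80% | 20.0% vs 44.0% | 24.0 points | 13.0% |
| 70% | 17.5% vs 38.5% | 21.0 points | 19.9% |

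With true rates of 25% in both arms, the chance rises from 82.0% with full recording to 89.8% at 70%. Equal under-recording therefore makes non-inferiority easier to declare. Unequal under-recording could push either way: more loss with cetirizine favours non-inferiority, more loss with diphenhydramine works against it.

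The table shows direction only. The documents give no share of IRRs that present with fatigue or dizziness alone, and no rate at which investigators would call them MS related.

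**The case against.** A reader might infer that the exemption hides the tolerability difference the trial is run to detect. The documents do not support that. SSS, VAS-F and TSQM are named secondary outcomes (Section 3.3.2), are taken after every infusion and are compared between arms at day 0, day 14 and week 24. No AE rule can remove those scores. AEs are only summarised, and no between-arm AE test is planned. Nor does the plan say that fatigue or dizziness is expected more often with diphenhydramine: Sections 1 and 3.2 speak of drowsiness and sedation, while Section 3.4 lists fatigue and dizziness as reactions to OCR.

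It can also be said that the two rules work in sequence: the exemption settles what is not an AE, and all AEs are then recorded. The definition in Section 5.1 rests on timing, so a symptom that begins after premedication fits it. Fatigue and dizziness are named IRR presentations, each infusion has its own reaction assessment and call, and there is a dedicated IRR form. Section 3.3.1 defines the primary outcome by reference to CTCAE and does not mention the exemption.

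Most of this stands, and it limits the point. What remains is that reading the rules in sequence depends on first deciding whether a symptom is MS related. The plan gives no criterion for that decision and no exception for the hours when a drug effect is most plausible. The exclusion of the studied condition in Section 5.1 makes it easier to set a worsened MS symptom aside. The scales cover neither the next day nor dizziness.

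**Conclusion.** The point holds in a limited form. As written, the exemption allows new or worse post-infusion fatigue, drowsiness or dizziness to be left out of the AE record on investigator opinion, in a trial with no masking described. The exposed data are next-day fatigue or drowsiness, dizziness at any time, and the descriptive summary by relationship to premedication. Loss from the primary IRR count is possible but not instructed; if it occurred equally in both arms, it would favour non-inferiority.

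The size cannot be estimated from the documents. The rise from 4.9% to between 8.3% and 19.9% rests on assumed recording shares of 90% to 70% and on true rates at the margin. The comparisons on SSS, VAS-F and TSQM, the sample size and the planned analyses all stay as they are. This is a cheap improvement to a recording rule, not a fault in the main comparison.

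**What to change.** Add to Sections 3.4 and 5 that the MS-symptom exemption does not apply to any symptom that starts or worsens from premedication until 24 hours after the OCR infusion, as collected at the infusion visit and the next-business-day call. Record each such symptom with onset, grade and relationship to premedication and to OCR separately, using the existing scale in Section 5, and assess it against the IRR definition. Keep the exemption for the rest of follow-up.

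The 24-hour limit matches the IRR window already in Sections 3.4 and 5. A window running to the call would extend over the weekend after a Friday infusion and bring in ordinary MS fluctuation. Symptoms that do prove to be MS can still be graded as unlikely or not related, so they need not inflate the attributed counts.

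The cost is a short addition in two places and more low-grade AE entries on three infusion days per patient. No change to sample size or analysis follows.

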### **Infusion-Related Reactions (IRRs)**

Adverse events that occur during or within 24 hours after OCR administration and are judged to be related to OCR infusion should be captured as a diagnosis (e.g., "infusion-related reaction" or "anaphylactic reaction") on the Adverse Event eCRF. If possible, avoid ambiguous terms such as "systemic reaction." Associated signs and symptoms should be recorded on the dedicated Infusion-Related Reaction eCRF. If a patient experiences both a local and systemic reaction to the same dose of OCR, each reaction should be recorded separately on the Adverse Event eCRF, with signs and symptoms also recorded separately on the dedicated Infusion-Related Reaction eCRF.

Investigators should consider a local IRR for any symptoms affecting the skin and localized to only one place. Any other IRR should be considered systemic.

### **Severity**

The adverse event severity grading scale for the NCI CTCAE (v5.0) will be used for assessing adverse event severity. The below table should be used for assessing severity for adverse events that are not specifically listed in the NCI CTCAE.

### **Adverse Event Severity Grading Scale for Events Not Specifically Listed in NCI CTCAE**

Grade	Severity
1	Mild; asymptomatic or mild symptoms; clinical or diagnostic observations only; or intervention not indicated
2	Moderate; minimal, local, or non-invasive intervention indicated; or limiting age-appropriate instrumental activities of daily living a
3	Severe or medically significant, but not immediately life-threatening; hospitalization or prolongation of hospitalization indicated; disabling; or limiting self-care activities of daily living b,c
4	Life-threatening consequences or urgent intervention indicated d
5	Death related to adverse event d

NCI CTCAE = National Cancer Institute Common Terminology Criteria for Adverse Events.

Note: Based on the most recent version of NCI CTCAE (v5.0), which can be found at:  
[http://ctep.cancer.gov/protocolDevelopment/electronic\\_applications/ctc.htm](http://ctep.cancer.gov/protocolDevelopment/electronic_applications/ctc.htm)

- a. Instrumental activities of daily living refer to preparing meals, shopping for groceries or clothes, using the telephone, managing money, etc.
- b. Examples of self-care activities of daily living include bathing, dressing and undressing, feeding oneself, using the toilet, and taking medications, as performed by patients who are not bedridden.
- c. If an event is assessed as a "significant medical event," it must be reported as a serious adverse event.
- d. Grade 4 and 5 events must be reported as serious adverse events.

### **Relationship to Premedication and OCR**

The relationship or association of the AE to the premedication and OCR will be characterized as follows:

Not related	Any event that does not follow a reasonable temporal sequence from administration of drug AND that is likely to have been produced by the patient's clinical state or other modes of therapy administered to the patient.
Unlikely	Any event that does not follow a reasonable temporal sequence from administration of drug OR that is likely to have been produced by the patient's clinical state or other modes of therapy administered to the patient.
Possibly	Any reaction that follows a reasonable temporal sequence from administration of drug OR that follows a known response pattern to the suspected drug AND that could not be reasonably explained by the known characteristics of the patient's clinical state or other modes of therapy administered to the patient.
Related	Any reaction that follows a reasonable temporal sequence from administration of drug AND that follows a known response pattern to the suspected drug AND that recurs with re-challenge, AND/OR is improved by stopping the drug or reducing the dose.

## 5.1 ASSESSMENT OF SAFETY

### Specification of Safety Variables

Safety assessments will consist of monitoring and reporting adverse events (AEs) and serious adverse events (SAEs) that are considered related to the premedication or OCR, per protocol. This includes all events of death, and any study specific issue of concern.

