### **Premature Termination Visit**

If OCR or the premedication is withdrawn and the patient is unwilling to continue in the trial for observation, complete a premature termination visit as soon as possible. If the patient discontinues from the study for any other reason noted in the patient discontinuation criteria, a premature termination visit must be performed as soon as possible. Patients who were withdrawn from the study for any reason will not be replaced. The following clinical and laboratory evaluations will be performed:

- Vital signs (blood pressure, heart rate, oral temperature, and weight)
- Neurological exam
- Estimated EDSS
- MFIS
- MSIS-29
- Concomitant medications and adverse events (AE reporting period continues 30 days following the last administration of study treatment or study discontinuation/termination, whichever is earlier. Reassess AEs via phone call at 30 days +7 from time of last dose or study termination.)
- Laboratory assessments:
  - CBC and LFTs
  - Serum immunoglobulins, quantitative
- Primary reason for discontinuation

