### **Adverse Event Reporting Period**

The study period during which all AEs and SAEs must be reported begins after informed consent is obtained and ends 30 days following the last administration of study treatment or study discontinuation/termination, whichever is earlier. After this period, investigators should only report SAEs that are attributed to prior study treatment.

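### Section 5.1 limits safety reporting to related events, against the all-AE rule elsewhere; separately, AE reporting closes before scheduled AE reviews for the few patients who stop treatment early

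*Combined protocol and SAP*

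**What the plan says.** **Scope.** Section 5.1 (Specification of Safety Variables) describes safety assessment as "monitoring and reporting adverse events (AEs) and serious adverse events (SAEs) that are considered related to the premedication or OCR, per protocol". It then adds: "This includes all events of death, and any study specific issue of concern". Section 3.4 sends the reader to section 5.1 for the full account of the safety evaluation.

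Other sections set a wider scope:
- Section 5, opening: "All AEs should be recorded in the patient's AE case report form regardless of severity or relationship to the premedication or OCR".
- Section 5.1, definition of an adverse event: an event counts "whether or not there is a causal relationship with OCR or the premedication".
- Section 5.2, Adverse Event Reporting Period: "The study period during which all AEs and SAEs must be reported begins after informed consent is obtained". The opening of section 5.2 and its paragraph on assessing AEs also speak of all AEs and SAEs, however they come to light.
- Section 5.3(i): SAEs unrelated to OCR go to the OCR manufacturer within 30 calendar days.
- Section 4.9.4: AEs are summarized by, among other things, their relationship to the premedication and to OCR.

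**Period.** Section 5.2 says that the reporting period "ends 30 days following the last administration of study treatment or study discontinuation/termination, whichever is earlier". After that, only SAEs attributed to earlier study treatment are reported. The same end rule appears in section 4.5.1 (Visit 4 and Premature Termination Visit) and in note J of Appendix A. AEs are on the assessment list at both of those visits. A patient whose OCR or premedication is withdrawn goes to premature termination if "the patient is unwilling to continue in the trial for observation", which implies that a willing patient may stay.

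**The concern.** An investigator who follows section 5.1 would report fewer events than one who follows section 5 or 5.2. Section 5.1 is also the section to which the protocol directs staff for safety detail. The filter it implies is not defined: the relationship table in section 5 has four levels, and section 5.1 does not say whether an event rated possibly related passes. Sections 4.2 and 4.3 describe no masking, and section 3.2 records the investigators' experience of marked drowsiness with diphenhydramine. A causality filter applied by people who know the assignment could therefore work differently in the two groups.

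On the period, a patient who has stopped treatment may still be in the study at Visit 4, where an AE review is scheduled, although the reporting period closed months before. Section 4.6 lists serious hypersensitivity and life-threatening infusion reactions among the reasons for stopping, so patients with a shortened period may include some who had reactions.

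**Working it through.** The plan states no figure on AE follow-up, so there is none to reproduce. The sample size of 26 per arm does not enter this point.

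**1. Scope, side by side.**

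| Place | Events covered |
|---|---|
| 5.1, Specification of Safety Variables | Related AEs and SAEs, all deaths, study-specific concerns |
| 5, opening | All AEs on the case report form, any relationship |
| 5.1, Adverse Events | Definition does not require causality |
| 5.2, three places | All AEs and SAEs |
| 5.3(i) | Includes SAEs unrelated to OCR |
| 4.9.4 | Summary by relationship, so unrelated events must be held |

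The first row is the outlier. An unrelated, non-fatal AE that is not a study-specific concern is outside it and inside the others (or, for section 5.3(i), inside if serious). The share of AEs this would remove cannot be calculated, because the plan gives neither AE rates nor the proportion expected to be unrelated.

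**2. End of the period, by last dose.** Inputs from section 4.5.1: day 0; Visit 3 at day 14 ± 2 (12 to 16); Visit 4 at 24 × 7 = day 168 ± 14 (154 to 182). Closing day = last dose + 30, unless the other date comes first.

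- Completer: 168 + 30 = day 198 (184 to 212) if the 30 days applies to both dates. Visit 4 falls inside the period.
- Last dose day 0, observed to Visit 4: closes on day 30. Gap = 168 − 30 = 138 days (154 − 30 = 124 to 182 − 30 = 152). Uncovered: 138/168 = 82%.
- Last dose day 14, observed to Visit 4: closes on day 44 (42 to 46). Gap = 168 − 44 = 124 days (154 − 46 = 108 to 182 − 42 = 140). Uncovered: 124/168 = 74%.
- Illustration, last dose day 14 and withdrawal on day 100: closes on day 44, and the termination visit asks for AEs 100 − 44 = 56 days later.

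The sentence can also be read with the 30 days attached only to the last dose. The early-stopper results do not change: in the illustration the earlier of 44 and 100, and the earlier of 44 and 130, are both 44.

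**3. Size across the trial.** The plan gives no discontinuation rate. Assume that 5% to 20% of the 52 patients (2.6 to 10.4) stop after day 0 or day 14 and are followed to week 24. Total follow-up is 52 × 168 = 8,736 person-days.

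- Low end: 2.6 × 124 = 322.4; 322.4/8,736 = 3.7%.
- High end: 10.4 × 138 = 1,435.2; 1,435.2/8,736 = 16.4%.

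So about 4% to 16% of person-days would fall outside the period, entirely on that assumed range.

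**4. An undefined term.** Study treatment is not defined in the reporting rule. Section 4.3 uses the term when describing the premedication arms, while section 4.6 lists separate stopping reasons for premedication and for OCR. If it means the premedication alone, a patient who stopped only that could receive a later OCR infusion after the period had closed.

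**The case against.** The strongest defence is that section 5.1 is one general sentence and every working instruction points the other way: record all AEs, define them without causality, report all of them, and send unrelated SAEs on a set timeline. Section 4.9.4 applies no related-only filter. On this view no event need be lost and the sentence only needs tidying. It stands to this extent: no loss has been shown, and section 5.1 already keeps all deaths. It does not remove the contradiction, because section 3.4 names section 5.1 as the reference for the safety evaluation.

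On the period, a reader might infer that the end rule conflicts with the week-24 AE review in general. The text does not support that. The Visit 4 list carries the same rule, and a completer is dosed at that visit. A reader might also infer a biased between-arm safety comparison. Section 4.9.4 plans a descriptive summary for all patients and states no test or by-arm display, so the exposure is an incomplete or inconsistent safety summary.

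Nor is everything after day 30 or 44 necessarily lost. AEs are still on the lists for Visit 4 and the termination visit, AEs of moderate or higher severity are followed to resolution or stabilization (section 5), and SAEs attributed to earlier treatment remain reportable (sections 5.2 and 5.3(f)). The defect is that the reporting rule and the visit schedule give different instructions for the same patients.

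**Conclusion.** The scope contradiction is established from the text and needs no assumption. Its effect on the number of events cannot be sized from the documents.

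The period problem is real for two groups only: patients who stop after day 0 or day 14 and stay for observation, and patients who withdraw more than 30 days after their last dose. It rests on reading the premature termination paragraph as allowing observation after stopping, which is implied and not stated. The 82% is the figure for one patient with a last dose on day 0, and should not be read as the share of trial follow-up at risk. The number of such patients is unknown and probably small.

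A reader might also fear for the primary endpoint. That is not supported: the day-0 infusion reaction is captured within 24 hours and at the next-business-day call, long before any period closes, and the sample size is unchanged. This is a minor point that is cheap to correct.

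**What to change.** 1. In section 5.1, replace the clause restricting assessment to related events with: regardless of relationship to the premedication or OCR.
2. In section 4.5.1 (Visit 4 and Premature Termination Visit), section 5.2 and note J of Appendix A, reconcile the end of the AE period with the scheduled reviews. State that for patients who remain in the study AEs are reported at least through their last study visit (Visit 4 or premature termination), without extending collection beyond what a withdrawn patient's consent allows.
3. In the same places, say whether study treatment means the premedication, OCR or both.

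Simply exchanging the earlier date for the later one is not enough. With a last dose on day 14 and withdrawal on day 100, reporting would run to 100 + 30 = day 130, after the patient has left and possibly after consent is withdrawn. It would also leave study treatment undefined.

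The cost is a few words in the protocol and slightly more AE recording for a few patients.
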